#### **10.5.2 To evaluate both formulations on change in serum ferritin in ICT naïve and pre-treated patients**

Absolute and relative change from baseline in serum ferritin for core phase will be summarized after 24 weeks (i.e. assessed at week 25 visit) and 48 weeks of treatment using standard descriptive statistics by treatment arm for the FAS-1 and FAS-2. The 95% confidence intervals for mean will additionally be provided.

A forest plots will be presented with change in SF after 24 weeks and 48 weeks of treatment and the corresponding exact 95%CI. Point estimates and 95% CI will be generated for the FAS-1, FAS-2 and FAS-3.

Furthermore, the mean and standard deviation values of serum ferritin will be plotted by treatment group and week.

### **10.5.3 To evaluate both formulations on patient satisfaction and palatability using PRO/ObsRO questionnaires**

The FAS-1, FAS-2 and the FAS-3 will separately be used for the analysis of patient satisfaction and palatability using a PRO/ObsRO questionnaire for the core phase.

For the SICT questionnaire, the score for each domain will be the mean of the score of items included in the corresponding domain. Standard descriptive analyses will be performed for both formulations for each domain score at Week 2, Week 3, Week 25 and the EOT (core)/777 visits as well as their absolute changes at Week 25 and EOT (core)/777 visits from Week 2. The standard descriptive analyses include: n, mean, standard deviation, minimum, median and maximum. The 95% confidence intervals for the absolute changes in all domains at Week 25 and EOT (core)/777 visits from Week 2 will be presented for both formulations.

For the palatability questionnaire the overall score will be constructed using a scoring matrix from the score of items. Standard descriptive analyses will be performed for both formulations for the overall score at the Week 2, Week 3, Week 25 visits, and last day of study drug intake and the absolute changes of the overall score at the Week 25 visit and last day of study drug from Week 2. The standard descriptive analyses include: n, mean, standard deviation, minimum, median and maximum. The 95% confidence interval for the absolute change of the overall score at the Week 25 visit and last day of study drug from Week 2 will be presented for both formulations.

Details about scoring and analyses will be included in the SAP.

### **10.5.4 To evaluate both formulations on overall safety, measured by frequency and severity of adverse events and changes in laboratory values**

[figure not shown]
The Safety Set 1, Safety Set 2 and the Safety Set-3 will separately be used. The overall observation period will be divided into three mutually exclusive segments:

1. Pre-treatment period: from day of patient's informed consent to the day before first dose of study medication
2. On-treatment period: from day of first dose of study medication to 30 days after last dose of study medication
3. Post-treatment period: starting at day 31 after last dose of study medication.

#### **10.5.4.1 Adverse events (AEs)**

Summary tables for adverse events (AEs) have to include only AEs that started or worsened during the on-treatment period, the treatment-emergent AEs. However, all safety data (including those from the pre and post-treatment periods) will be listed and those collected during the pre-treatment and post-treatment period are to be flagged.

The incidence of treatment-emergent adverse events (new or worsening from baseline) will be summarized by system organ class and/or preferred term, severity, type of adverse event, relation to study treatment by formulation group. Exposure-adjusted adverse event incidence, defined as number of patients with new or worsened AEs during period/[total number of days patient was on treatment summed for all patients/365.25 days], will be presented.

An overall summary of type of AEs (e.g. serious, leading to study drug discontinuation, requiring dose adjustment or/and interruption) will be presented by severity and formulation group.

Specific groupings of adverse events of special interest will be considered and the number of patients with at least one event in each grouping will be reported. Such groups consist of adverse events for which there is a specific clinical interest in connection with Deferasirox treatment or adverse events which are similar in nature (although not identical). Note that certain adverse events may be reported within multiple groupings/AESIs.

AESIs are defined by MedDRA terms. All AESI definitions or AE groupings are specified in the Novartis electronic Case Retrieval Strategy (eCRS). The latest version of the eCRS available at the time of the analysis will be used.

Incidence of AESI will be summarized by grouping, preferred term and treatment arm.

Summary tables for adverse events (AEs) will be repeated for the optional extension phase on the Safety Set 4.

#### **10.5.4.2 Laboratory abnormalities**

All laboratory values will be converted into SI units and the severity grade calculated using the low/normal/high classifications based on laboratory normal ranges and for selected parameters (see [Table 10-1](#) below) by notable/extended ranges.

The following summaries will be generated separately for hematology, biochemistry and urinary laboratory tests:

- shift tables using normal/notable/extended ranges to compare baseline to the worst on-treatment value
- listing of all laboratory data with values flagged to show the corresponding normal/notable/extended ranges (see [Table 10-1](#) below).

For laboratory parameters observed values (and changes from baseline), and per subsequent quarter will be summarized by descriptive statistics overtime (n, mean, standard deviation, minimum, lower quartile, median, upper quartile and maximum).

Laboratory abnormalities will be described for the optional extension phase on the Safety Set 4.

In addition to the above mentioned tables and listings, other exploratory analyses, for example figures plotting time course of raw or change in laboratory tests over time or box plots might be specified in the SAP.

**Table 10-1 Definition of notable/extended ranges for laboratory tests**

Laboratory test	Criteria for notable ranges
Platelet count	< 100 x 10  /L (extended range <50×10  /L)
Absolute neutrophils	< 1.5 x 10  /L (extended range <0.5×10  /L)
Serum creatinine	> 33% increase from baseline and > ULN at two consecutive measurements at least 7 days apart
Creatinine clearance	<60 mL/min at two consecutive measurements at least 7 days apart (extended range <40 mL/min at two consecutive measurements at least 7 days apart)
Urinary protein/urinary creatinine ratio	≥ 1.0 (mg/mg) at two consecutive measurements at least 7 days apart
ALT and AST	>5 x ULN and >2 x baseline value (extended range >10×ULN and >2×baseline value)

### 10.5.5 To evaluate compliance using a daily PRO/ObsRO questionnaire

Patient adherence to medication regimen instructions will be assessed via daily diary records (PRO / ObsRO questionnaire) providing information on two dimensions: whether the study medication is consumed and the time of medication intake. These data will be summarized over time by descriptive statistics for both formulations. The rate of dosing instructions deviations (doses missed completely or not taken at approximately the same time every day) will be calculated for each study arm.

The FAS-1, FAS-2 and FAS-3 will separately be used for the analysis of compliance using a daily PRO/ObsRO questionnaire.

Details about scoring and analyses will be included in the SAP.

### 10.5.6 Pharmacokinetics

The PAS will be used to summarize (pre-dose) Cmin and (post-dose) Cmax concentrations and to assess patients' compliance and analysis of PK concentrations. PK/PD (PK/safety and PK/Efficacy) analyses will be based on the Safety Set or FAS accordingly. Other analyses and listings of PK concentration will use the FAS.

#### 10.5.6.1 To evaluate pre-dose PK data to support the assessment of compliance

Pre-dose PK concentrations (Cmin) from the PAS will be analyzed to support the assessment of compliance. Predicted individual Cmin concentrations will be derived from a power model considering dose and potential other covariates, such as body weight. Predicted individual Cmin concentrations will be compared to respective observed pre-dose concentrations at steady-state of all patients. Distributions of the difference between predicted and observed Cmin values will be shown graphically by boxplots for both treatment groups and visit.

#### 10.5.6.2 Description of individual PK concentrations and parameters

PK concentrations will be summarized by treatment, visit and time point. PK parameters will be summarized by treatment and visit.

Descriptive statistics of PK concentration and PK parameters will include arithmetic and geometric means, median, SD, CV%, CV% of the geometric mean, minimum and maximum. Zero concentrations will not be included in the geometric mean calculation.

All analyses will be based on the PAS.

#### **10.5.6.3 To explore PK/PD relationship**

Serum ferritin change from baseline will be fitted by a linear mixed effect model with log-transformed matching pre-dose concentrations as covariates and subject as random effect.

Serum creatinine change from baseline, serum creatinine clearance change from baseline and urine protein creatinine ratio change from baseline will be fitted by a linear mixed effect model with log-transformed matching pre-dose and post-dose concentrations respectively as covariates and subject as random effect.

Incidence of notable serum creatinine events as defined in [Table 10-1](#) will be analyzed by a logistic regression fitted by GEE methods as appropriate including matching log-transformed pre- and post-dose concentrations, respectively.

Incidence of notable serum creatinine clearance events as defined in [Table 10-1](#) will be analyzed by a logistic regression fitted by GEE as appropriate methods including matching log-transformed pre- and post-dose concentrations, respectively.

For all statistical models other covariates such as demographic characteristics may be included if appropriate.

Other non-linear mixed effect models, such as effect-compartment models, may be established if appropriate to further explore exposure efficacy or safety relationship and will be reported separately.

#### **10.5.6.4 Data handling principles**

Biofluid concentrations will be expressed in mass per volume units. All concentrations below the limit of quantitation or missing data will be reported as such in the concentration data listings. Concentrations below the limit of quantitation will be treated as zero in summary statistics.

### **10.6 Other analyses**

#### **10.6.1 Other safety data**

Data from vital signs, body weight, ECG, echocardiogram, ocular, and auditory examinations will be listed and summarized with descriptive statistics as appropriate separately for each Safety Set. All new or worsened abnormalities will be recorded on the AE eCRF page.

##### **10.6.1.1 Cardiac evaluation**

ECG and Echocardiogram will be performed at baseline and EOT in the core phase. ECG will be performed when clinically indicated during the optional extension phase. Abnormalities will be reported together with an overall interpretation of the findings. Any abnormalities at baseline will be summarized. At post-baseline assessment, the investigator will flag all abnormalities s will be recorded

on the AE eCRF page. All findings of patients with new or worsened clinically significant abnormalities will be listed.

### 10.6.1.2 Vital signs and body weight

Measurements of vital signs and body weight done more than 30 days after discontinuation of study medication will be excluded from the analysis but will be listed.

The change from baseline in diastolic blood pressure, systolic blood pressure, pulse rate, and weight will be summarized by scheduled visit with n, mean, SD, minimum, median, and maximum values.

A listing will be provided for all vital signs and weight. Notable pulse rate and weight values are flagged. The criteria for notably abnormal pulse rate and weight are displayed in [Table 10-2](#).

**Table 10-2** Definition of notable ranges for pulse rate and weight

Parameter		
Weight	High	Increase from baseline $\geq 10\%$
	Low	Decrease from baseline $\geq 10\%$
Pulse rate (beats per minute)	High 	12-18 months > 140 18-24 months > 135 2-3 years > 128 3-4 years > 123 4-6 years > 117 6-8 years > 111 8-12 years > 103 12-15 years > 96 15-18 years > 92
	Low 	12-18 months < 103 18-24 months < 98 2-3 years < 92 3-4 years < 86 4-6 years < 81 6-8 years < 74 8-12 years < 67 12-15 years < 62 15-18 years < 58

: Fleming et al 2011.

### 10.6.1.3 Auditory and ocular assessment evaluations

Auditory evaluations will be performed at baseline, visit 17 if entering the optional extension phase and annually during the optional extension phase and ocular evaluations at baseline, Week 25 visit (Visit 11) and at EOT(core) visit (Visit 777) during the core phase and annually

during the optional extension phase. Any abnormalities at baseline will be summarized. Abnormalities will be reported together with an overall interpretation of the findings. All new or worsened abnormalities will be recorded on the AE eCRF page. All findings of patients with new or worsened clinically significant abnormalities will be listed.

#### **10.6.1.4 Growth and Development**

For pediatric patients, growth velocity and pubertal stage will be listed at baseline, at EOT visit 777 and annually during the optional extension phase and summarized using descriptive statistics as appropriate.

#### **10.6.1.5 Serum ferritin during the optional extension phase**

Change from baseline in serum ferritin at every year will be described for the Safety Set 4.

### **10.7 Interim analysis**

One interim analysis has been added to allow for early analysis of the core phase data if requested by the health authority. All chelation-naïve patients randomized in the study and who have completed a minimum of 12 weeks of treatment exposure or discontinued from treatment core phase at the time of the cutoff date will be included in the interim analysis.

All the analyses included in the interim analysis will be descriptive. Testing of hypotheses will not be performed and no decisions regarding the future course of the trial is anticipated at the time of the IA and the trial will continue. Therefore adjustment for multiplicity is not performed.

Descriptive statistics will be provided by treatment arm on the primary endpoints (i.e. change from baseline in serum ferritin and compliance measured by stick pack /tablet count) and key safety data.

Details on the analyses will be described in the statistical analysis plan.

### **10.8 Sample size calculation**

The primary objective of this study is to evaluate patient compliance (using stick packs or tablets counts) and change in serum ferritin (SF) over time for both formulations of deferasirox in pediatric ICT naïve patients with iron overload.

The sample size was estimated to demonstrate superiority and statistical significance for both co-primary endpoints.

The assumptions made for this study were:

- For serum ferritin:

An expected improvement between both formulations in SF change from baseline after 24 weeks of treatment of  $-450\text{ng/mL}$  with a standard deviation (SD) of  $900\text{ ng/mL}$  based on results from study CICL670A0107 in pediatric patients treated with Exjade on  $\geq 25\text{ mg/kg/day}$  after 24 weeks of treatment.

- For compliance using stick packs or tablets counts:

An expected improvement between both formulations in mean relative consumed tablet count of 10% with a SD equal to 17.625% based on the pooled analysis on pediatric patients (77) from Exjade studies [\[ICL670A2206\]](#) (39), [\[ICL670A2204\]](#) (24) and [\[ICL670A2214\]](#) (14).

The sample size, driven by the calculation of serum ferritin, has been determined to obtain 76% power at a one-sided 5% level of significance for showing superiority of granule formulation over DT formulation with respect to change from baseline after 24 weeks of treatment in serum ferritin.

A sample size of 45 in each group will have 76% power to detect a difference in means of 400.0 ng/mL assuming that the common SD is 800.0 ng/mL using a two group t-test with a 0.050 one-sided significance level. With 45 patients per arm, the power to detect a difference of 10% or more in mean compliance is about 84%.

Considering a potential of 5% dropout rate patients, the required sample size to achieve the primary objective is 48 chelation naïve patients for each treatment group (96 patients in total).

In addition, the clinical trial will enroll patients previously treated with iron chelation patients. Considering that a direct comparison of granule and DT formulations in terms of efficacy is not foreseen in previously chelated patients, the required sample size is not based on power calculations as usual. The selection of number of patients is based on the precision in the estimate of SF change after 48 weeks of treatment and on practical considerations.

A maximum of 120 (60 patients will be in each formulation group) previously chelated patients will be enrolled. Sixty patients will provide an estimate of SF change with precision (half-width of 95% confidence interval) equal to 303.6.

**Table 10-3** below lists the precisions in the estimates of SF change for different numbers of patients using the estimated SD obtained from the [\[CICL670A0107\]](#) study results in pediatric patients treated with Exjade on  $\geq 25$  mg/kg/day at week 48 of treatment.

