	
least one evaluable pre or post-dose PK concentration (deferasirox). More details are provided in Section 10.1.4.
 
Statistical Analyses:
 
Primary efficacy endpoints: All analyses for the primary objective will be performed based on core period and on the FAS-1 and presented by treatment group: deferasirox DT and deferasirox granule formulation. The co-primary efficacy variables are:
 

• Compliance measured by stick pack /tablet count based on amount of medication dispensed, returned and reported as lost/wasted by the patient or caregiver over 24 weeks of treatment (i.e. assessed at week 25 visit). Compliance will be calculated as the ratio of total count consumed to total count prescribed, where

• total count consumed is derived from cumulative dispensed, returned and lost/wasted counts over 24 weeks of treatment (i.e. assessed at week 25 visit);

• total count prescribed is cumulative prescribed count over 24 weeks of treatment (i.e. assessed at week 25 visit).

• Change from baseline in serum ferritin after 24 weeks of treatment (i.e. serum ferritin assessment at week 25 visit).

 
The primary efficacy analysis will be the comparison of means between the two treatment arms of change from baseline after 24 weeks of treatment in SF and mean relative consumed stick pack /tablet count over 24 weeks of treatment. Analysis of covariance (ANCOVA) will be performed for comparison between treatment groups at a one-sided 5% level of significance. The ANCOVA model for compliance endpoint will include treatment group and age group (2 to <10 years, 10 to <18 years), as factors. The model for serum ferritin endpoint will also include the serum ferritin value at baseline as covariate.
 
The trial will be claimed successful if the superiority of granule formulation relative to DT formulation could be demonstrated with regard to both endpoints. Therefore, no adjustment of the type I error (alpha) is required.
 
Sample size calculation: The primary objective is to evaluate patient compliance (using stick packs or tablets counts) and change in serum ferritin (SF) over time for both formulations of deferasirox in pediatric ICT naïve patients with iron overload after 24 weeks of treatment.
 
The sample size was calculated to show superiority of the granule formulation relative to DT formulation with regard to both co-primary endpoints.
 
The assumptions made for this study were as follows:
 

• For serum ferritin: An expected improvement between both formulations in SF change from baseline after 24 weeks of treatment of -450 ng/mL with a standard deviation (SD) of 900 ng/mL based on results from study CICL670A0107 in pediatric patients treated with Exjade on <math>\geq 25</math> mg/kg/day after 24 weeks of treatment.

• For compliance over 24 weeks of treatment using stick packs or tablets counts: An expected improvement between both formulations in mean relative consumed tablet count of 10% with a SD equal to 17.625% based on the pooled analysis on pediatric patients (77) from Exjade studies [ICL670A2206] (39), [ICL670A2204] (24) and [ICL670A2214] (14).

 
The sample size driven by the calculation for serum ferritin, has been determined to obtain 76% power at one-sided 5% level of significance for showing superiority of granule formulation over DT formulation with respect to change from baseline after 24 weeks of treatment in serum ferritin, assuming a dropout rate of 5%.
 
A sample size of 48 in each group will have 76% power to detect a difference in means of 400.0 ng/mL assuming that the common SD is 800.0 ng/mL using a

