--	---

two group t-test with a 0.050 one-sided significance level. With 48 patients per arm, the power to detect a 10% difference in mean compliance is about 84%.

In addition, the clinical trial will enroll patients previously treated with iron chelation. Considering that a direct comparison of granule and DT formulations in terms of efficacy is not foreseen in previously chelated patients, the required sample size is not based on power calculations as usual. The selection of number of patients is based on the precision in the estimate of SF change at 48 weeks of treatment and on practical considerations.

A maximum of 120 patients (60 patients will be in each formulation group) previously chelated patients will be enrolled. Sixty patients will provide an estimate of SF change with precision (half-width of 95% confidence interval) equal to 303.6.

The table below lists the precisions in the estimates of SF change for different numbers of patients using the estimated SD obtained from the CICL670A0107 study results in pediatric patients treated with Exjade on  $\geq 25$  mg/kg/day at week 48 of treatment.

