#### **10.4.2 Statistical method of analysis**

The primary efficacy analysis will be the comparison of means between the two treatment arms of change from baseline after 24 weeks of treatment in SF and mean relative consumed stick pack /tablet count over 24 weeks of treatment.

The trial will be claimed successful if the superiority of granule formulation relative to DT formulation could be demonstrated with regard to both endpoints. Therefore, no adjustment for multiplicity of the type I error (alpha) is required.

The primary inferential analysis described below will be based on the FAS-1.

Let  $\mu_{SF,G}$  and  $\mu_{SF,DT}$  denote the mean change from baseline in SF to week 25 visit for granule and DT formulations, respectively. Let  $\mu_{C,G}$  and  $\mu_{C,DT}$  be similarly defined for compliance measured by stick pack /tablet count.

The null and the alternative hypothesis are defined as follows:

$H_0,SF: \mu_{SF,G} = \mu_{SF,DT}$  no effect of granule formulation with regard to change in SF, and/or

$H_0,C: \mu_{C,G} = \mu_{C,DT}$  no effect of granule formulation with regard to compliance

versus

$H_1,SF: \mu_{SF,G} < \mu_{SF,DT}$  mean change in SF favorable for granule formulation compared to DT formulation, and

$H_1,C: \mu_{C,G} > \mu_{C,DT}$  mean compliance favorable for granule formulation compared to DT formulation

Analysis of covariance (ANCOVA) will be performed for comparison between both treatment groups. The ANCOVA model for compliance endpoint will include treatment group and age group (2 to <10 years, 10 to <18 years) as factors. The model for serum ferritin endpoint will also include the serum ferritin value at baseline as covariate.

For each of the endpoint the following estimates from the ANCOVA will be provided:

- the least squares mean with 2-sided 95% confidence interval for each treatment arm
- the least squares means with 2-sided 95% confidence interval, p-value for the difference between treatment arms

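### The protocol summary attaches the 45-per-arm powers (76%, 84%) to 48 per arm, and no section gives the power for success on both endpoints, about 64% to 69% on the plan's own t-test

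*Protocol*

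**What the plan says.** **Success rule.** Protocol 10.4.2 states: "The trial will be claimed successful if the superiority of granule formulation relative to DT formulation could be demonstrated with regard to both endpoints". SAP Amendment 3 section 2.8.2 repeats the rule.

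**Claimed basis of the sample size.** Protocol 10.8 and SAP 2.11 both say: "The sample size was estimated to demonstrate superiority and statistical significance for both co-primary endpoints". The protocol summary says: "The sample size was calculated to show superiority of the granule formulation relative to DT formulation with regard to both co-primary endpoints". Section 10.8 adds that "the required sample size to achieve the primary objective is 48" chelation-naïve patients per group. All three texts also say that ferritin drives the number, and the 76% is tied to superiority "with respect to change from baseline after 24 weeks of treatment in serum ferritin".

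**Powers given.** Section 10.8 and SAP 2.11 attach 76% (ferritin) to 45 per arm. For compliance, 10.8 says: "With 45 patients per arm, the power to detect a difference of 10% or more in mean compliance is about 84" per cent, and SAP 2.11 says the same. Both then allow for 5% dropout to reach 48 per arm.

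The protocol summary gives the same two powers for a different number: "A sample size of 48 in each group will have 76% power to detect a difference in means of 400.0 ng/mL", and "With 48 patients per arm, the power to detect a 10% difference in mean compliance is about 84" per cent. The test is the same in all three places, a two-group t-test at one-sided 5%.

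No section gives a power for meeting both endpoints or a correlation between them. The interim predictive probability of success (SAP 4.6.3) covers ferritin only.

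**The concern.** There are two separate points.

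1. The summary and 10.8 give identical powers, from the same test and inputs, for different sample sizes. Both cannot be right.
2. The sample-size texts say the trial was sized for both co-primary endpoints, but neither stated power is the power of that rule. When both tests must succeed, the chance of success is at most the smaller of the two powers, and generally lower. A reader who takes 76% as the planned chance of meeting the primary objective is taking a ceiling for an estimate.

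This matters for reading the record. The End of Core Phase SAP (Table 1-1) reports that the primary objective was not met, without saying which endpoint failed. Planned power is useful context beside the treatment differences and 95% confidence intervals specified in 10.4.2. It does not explain the result.

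**Working it through.** **Inputs (Protocol 10.8, SAP 2.11)**
- Two-group t-test, one-sided 0.05, equal arms.
- Ferritin: difference 400 with SD 800 (power sentence in 10.8), or 450 with SD 900 (assumptions in 10.8 and SAP 2.11). Both give a standardised effect d = 0.5.
- Compliance: difference 10 points, SD 17.625, so d = 10/17.625 = 0.5674.
- Dropout 5%.

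**Formula.** Power = P(T > t₀.₉₅,df), where T is noncentral t with df = 2n − 2 and noncentrality d√(n/2).

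**Step 1: reproduce the plan at 45 per arm** (df 88, critical value 1.662)
- Ferritin: noncentrality 0.5 × √22.5 = 2.372; power 76.1% (plan: 76%).
- Compliance: noncentrality 0.5674 × √22.5 = 2.691; power 84.7% (plan: about 84%).
- Dropout: 45/0.95 = 47.4, rounded up to 48.

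The figures in 10.8 and SAP 2.11 are confirmed.

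**Step 2: the same test at 48 per arm** (df 94, critical value 1.661)
- Ferritin: 0.5 × √24 = 2.449; power 78.4%.
- Compliance: 0.5674 × √24 = 2.780; power 86.7%.

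The summary's 76% and 84% are therefore the 45-per-arm powers. Read literally, they are too low by 2.4 and about 2.7 points.

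**Step 3: power for both endpoints**
- Independent endpoints: the product. At 45: 0.7607 × 0.8475 = 0.645. At 48: 0.7843 × 0.8675 = 0.680.
- Correlated endpoints: simulation of the two t-tests, 2,000,000 draws per setting. The correlations are assumptions.
- No correlation assumption: lower limit p₁ + p₂ − 1, upper limit min(p₁, p₂). At 45: 0.7607 + 0.8475 − 1 = 0.608, and 0.761. At 48: 0.7843 + 0.8675 − 1 = 0.652, and 0.784.

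| Per arm | Ferritin | Compliance | Both, corr. 0 | Both, corr. 0.2 | Both, corr. 0.5 | Both, corr. 0.8 | Both, no assumption |
|---|---|---|---|---|---|---|---|
| 45 | 76.1% | 84.7% | 64.5% | 66.0% | 68.8% | 72.6% | 60.8% to 76.1% |
| 48 | 78.4% | 86.7% | 68.0% | 69.4% | 71.9% | 75.4% | 65.2% to 78.4% |

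**Step 4: how much ANCOVA would have to contribute.** Holding compliance power and the correlation fixed, I found the share of ferritin variance that the baseline covariate would need to remove for both-endpoint power to reach 76%. At 45 per arm it is about 35% (independent) or 25% (correlation 0.5). At 48 it is about 25% or 15%. The documents give nothing from which the actual reduction could be estimated.

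**The case against.** The case for leaving the text alone has real substance.

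- **The slip is small and errs low.** The sentence before it in the summary mentions 5% dropout, so 48 can be read as patients randomised. But the sentence itself gives a t-test power for 48 in each group, and the summary's power statement never mentions 45. It still conflicts with 10.8 and SAP 2.11.
- **The 76% is always labelled as ferritin power.** This is true, and nothing presents it as power for overall success. A statistician could derive the limits from the printed figures. The gap is that texts claiming to size for both endpoints stop short of stating that power.
- **The correlation of 0.5 is assumed.** It is, and so is any other value. The study's premise that better compliance lowers iron burden suggests a positive correlation but does not supply a number. The limits of 60.8% and 76.1% need no such assumption.
- **More than 45 per arm may be analysed.** Protocol 10.4.3 carries ferritin forward, and SAP 2.8.3 keeps early discontinuers in the compliance endpoint. The 48-per-arm row shows the effect, but only if those patients carry the full 24-week benefit.
- **The planned test is ANCOVA, which could raise power.** This stands as a caveat. The plan's own power statements rest on the t-test, so that is the basis for comparison.
- **The primary analysis is complete.** That limits the practical consequence. Even so, the later SAPs still refer readers to SAP 2.11 for the sample size.

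These objections bear on weight. None removes either point.

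**Conclusion.** Both points hold. The summary mislabels the powers. This is a minor error in the conservative direction and does not affect the design size of 48 per arm.

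The omission matters more. Under the planning t-test at 45 evaluable per arm, the chance of meeting the stated success rule is about 64% with independent endpoints and about 69% at an assumed correlation of 0.5. That is roughly 12 and 7 points below the ferritin power. The ferritin power could be attained only in the most favourable case.

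These figures assume the plan's effects and SDs, 45 analysed per arm, and the t-test rather than the ANCOVA that will be used. The single-endpoint figures in 10.8 and SAP 2.11 are correct as stated.

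**What to change.** 1. **Protocol summary:** attach 76% and about 84% to 45 evaluable patients per arm (48 randomised, 5% dropout), in line with 10.8 and SAP 2.11.
2. **Protocol 10.8, protocol summary and SAP 2.11:** add a sentence such as:

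   > Power for success on both endpoints, by the two-group t-test with 45 per arm, is lower than the ferritin power: about 64% if the endpoints are independent and about 69% at an assumed correlation of 0.5.

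   A clause noting that the baseline-adjusted ANCOVA may give higher power, by an unquantified amount, would be a fair addition.
3. **Consistency only:** use one ferritin difference and SD pair throughout. 400/800 and 450/900 give the same power.

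The End of Core Phase SAP and the final SAP refer back to 2.11 and need no edit of their own. The cost is wording: no change to enrolment, alpha or analysis. The sponsor would be showing a less favourable figure than the one now printed.
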